### 8.1 Inclusion Criteria

1. Subject's legally appointed and authorized representative (e.g., parent or legal guardian) will sign and date an informed consent form (ICF) and the subject will sign and date an assent form (if applicable).
  2. Subject's legally appointed and authorized representative (e.g., parent or legal guardian) is willing and able to comply with scheduled visits, treatment plan, study restrictions, laboratory tests, and other study procedures.
  3. Subjects (male and female) will be between the ages of 2 and 5 years, inclusive, on the date of informed consent (and assent, if applicable).
  4. Subjects who weigh  $\geq 8$  kg without shoes and wearing light clothing at the Screening Visit.
  5. Subjects with confirmed diagnosis of CF, defined as:
    - a sweat chloride value  $\geq 60$  mmol/L by quantitative pilocarpine iontophoresis as documented in the subject's medical record OR from the sweat chloride test result obtained at the Screening Visit (if an eligible historical sweat chloride result is documented in the subject's medical record, that result alone [and not the Screening Visit result] may be used to determine eligibility)
- AND
- clinical manifestations of CF.
6. Subjects who are homozygous for *F508del* (genotype to be confirmed at the Screening Visit or as documented in the subject's medical record).
  7. Subjects with stable CF disease as deemed by the investigator at the Screening Visit.
  8. Subjects who are willing to remain on a stable CF medication regimen through the Safety Follow-up Visit, if applicable.

## 8.2 Exclusion Criteria

1. History of any illness or comorbidity reviewed at the Screening Visit that, in the opinion of the investigator, might confound the results of the study, interfere with or pose an additional risk in conducting the study assessments, or pose an additional risk in administering study drug to the subject. For example, a history of cirrhosis with portal hypertension, or prior allergic reaction to gadolinium (Gd)-based contrast material, or metallic implants incompatible with MRI.
2. Any clinically significant laboratory abnormalities at the Screening Visit that would interfere with the study assessments or pose an undue risk for the subject (as deemed by the investigator).
3. Any of the following abnormal laboratory values at the Screening Visit:
  - Hemoglobin <10 g/dL
  - Alanine transaminase (ALT), aspartate transaminase (AST), or total bilirubin >2 × upper limit of normal (ULN)
  - Abnormal renal function defined as glomerular filtration rate  $\leq 45$  mL/min/1.73 m^2 (calculated by the Bedside Schwartz equation)
4. An acute upper or lower respiratory infection, PEx as defined by the investigator, or changes in therapy (including antibiotics) for pulmonary disease within 28 days before Day 1 (first dose of study drug).
5. Any clinically significant "non-CF-related" illness within 2 weeks before Day 1. "Illness" is defined as an acute (serious or nonserious) condition (e.g., gastroenteritis).
6. History of solid organ or hematological transplantation.
7. Ongoing or prior participation in an investigational drug study (including studies investigating LUM and/or IVA) within 30 days of the Screening Visit.
  - A washout period of 5 terminal half-lives of the previous investigational study drug, or 30 days, whichever is longer, must elapse before the Screening Visit.
  - The duration of the elapsed time may be longer if required by local regulations.

Note: Ongoing participation in a noninterventional study (including observational studies) is permitted.
8. Use of restricted medication or food within specified duration before the first dose of study drug as defined in Section 9.4.
9. Inability of the subject to perform the multiple-breath washout (MBW) assessment during the Screening Period (Section 11.4.2).
10. History of cataract/lens opacity or evidence of cataract/lens opacity determined to be clinically significant by a licensed ophthalmologist during the ophthalmologic examination (OE) at the Screening Visit. The Screening Visit OE does not need to be repeated if there is documentation of an examination meeting protocol criteria that was conducted within 3 months before the Screening Visit. Subjects with documentation of bilateral lens removal do not need the OE and this criterion does not apply.

[figure not shown]
11. The subject or a close relative of the subject is the investigator or a subinvestigator, research assistant, pharmacist, study coordinator, or other staff directly involved with the conduct of the study.

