### 3 SCHEDULE OF ASSESSMENTS

**Table 3-1 Study VX16-809-121: Screening**

Assessment	Screening Visit Day -28 through Day -1
Informed consent/assent	X
Demographics	X
Medical history	X
Medications review a	X
Stature, weight, and vital signs b,c	X
OE d	X
Full physical examination	X
CFTR genotype e,f	X
Serum chemistry f	X
Hematology f	X
Sweat chloride h	X
MBW i	X
Adverse events	Continuous from signing of ICF through Safety Follow-up Visit (if required)

BMI: body mass index; *CFTR*: cystic fibrosis transmembrane conductance regulator gene; [REDACTED];  
ICF: informed consent form; MBW: multiple-breath washout; OE: ophthalmological examination

- a All medications taken within 28 days before the first dose of study drug through the end of the study will be recorded (Section 9.5).
- b If children can stand unassisted and follow directions, stature should be measured as height; otherwise, stature will be measured as length. Stature and weight must be measured with shoes off and while wearing light clothing. BMI will be derived from this assessment. Refer to Section 11.5.4 for details.
- c The subject should rest for at least 5 minutes before having vital signs measured.
- d An OE will be conducted by a licensed ophthalmologist or optometrist. The examination does not need to be repeated if there is documentation of an examination meeting protocol criteria that was conducted within 3 months before the Screening Visit. Subjects with documentation of bilateral lens removal do not need the OE. Refer to Section 11.5.5 for details.
- e Subjects without a documented genotype in their medical record will be tested to assess *CFTR* genotype (see inclusion criterion 6 [Section 8.1]).
- f Refer to Section 11.5.2 for details.

- h If an eligible historical sweat chloride result is documented in the subject's medical record, that result alone (and not the Screening Visit result) may be used to determine eligibility (see inclusion criterion 5 [Section 8.1]). For subjects using an historical sweat chloride value documented in their medical record to determine eligibility, the sweat chloride test at the Screening Visit is still required. Refer to Section 11.4.3 for details.

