**Table 3-2 Study VX16-809-121: Treatment Period and Safety Follow-up Visit**

Event/Assessment a	Treatment Period									ETT Visit b	Safety Follow-up Visit c
	Part 1: Placebo-controlled Period				Part 1/ Part 2 d	Part 2: Open-label Period e					
	Day 1	Day 3 (± 1 Day)	Day 15 (± 3 Days)	Weeks 12, 24, 36 (± 7 Days)	Week 48 (± 7 Days)	Day 338 f (± 1 Day)	Day 350 (± 3 Days)	Weeks 60, 72, 84 (± 7 Days)	Week 96 (± 7 Days)		
Clinic visit	X		X	X	X		X	X	X	X	X
Telephone contact g		X				X					
Randomization h	X										
Stature and weight i	X		X	X	X		X	X	X	X	X
Vital signs j	X k		X	X	X k		X	X	X	X	X
OE l					X m				X m,n	X m,n	X m,n
Full PE o	X			Week 24	X			Week 72	X	X	X

- a Assessments will be performed before study drug dosing unless noted otherwise (Section 11.1).
- b If the ETT Visit occurs 10 days or later after the last dose of study drug, the Safety Follow-up Visit will not be required. Subjects who prematurely discontinue study drug treatment for AEs should be followed until the AE is considered resolved.
- c The Safety Follow-up Visit is required for 1) subjects who complete their ETT Visit <10 days after the last dose of study drug and 2) subjects who interrupt study drug treatment and complete their Week 96 Visit <10 days after the last dose of study drug; it is not required for subjects who continue onto commercially available, physician-prescribed LUM/IVA within 2 weeks (± 4 days) of completing study drug treatment at the Week 96 or ETT Visit.
- d The first open-label dose of LUM/IVA will be the dose administered at the Week 48 Visit after completion of the predose assessments.
- e If the subject's Week 48 Visit is delayed, all subsequent visits must be delayed accordingly based on the actual Week 48 Visit date.
- f The Day 338 Visit (telephone contact) should occur 1 to 3 days after the actual date of the Week 48 Visit, regardless of whether it is Study Day 338.
- g Telephone contacts will be made to assess the subject's status, any AEs, medications, treatments, and procedures.
- h Randomization must only occur after all inclusion and exclusion criteria are met and before the first dose of study drug. Randomization will be done through IWRS and may occur on Day -1.

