## 8 STUDY POPULATION

Eligibility will be reviewed and documented by an appropriately qualified member of the investigator's team before subjects are enrolled.

Subjects who meet all of the inclusion criteria and none of the exclusion criteria will be eligible for the study.

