### 9.1.1.3 Extension of Screening Period Window

A subject may have the Screening Period window extended by 1 week after approval by the medical monitor or authorized designee for the following reasons:

- Repetition of the Screening Period assessments (Section 9.1.1.1)
- To account for exclusionary events that may not reflect the subject's true baseline due to an acute event, which may resolve
- Scheduling of OE (Section 11.5.5)
- Availability or malfunction of required equipment, or technician error.

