MBW Assessment: LCI will be derived from MBW testing. LCI is a measure of ventilation inhomogeneity that is based on tidal breathing techniques that have been evaluated in patients as young as infants. Studies have shown that LCI correlates with forced expiratory volume in 1 second (FEV1) in its ability to measure airway disease in patients with mild to moderate lung disease, but can also detect lung disease at an earlier stage than spirometry. Furthermore, data from Study VX10-770-106 in subjects with CF with an FEV1 >90% showed LCI to be a more sensitive outcome measure than FEV1. LCI has also been shown to be a sensitive measure of lung function in subjects aged 6 to 11 years with high baseline lung function treated with LUM/IVA combination therapy, as shown by the results of Studies VX14-809-109 and VX13-809-011B, and has demonstrated that early intervention with LUM/IVA can improve lung function in the pediatric CF population. Given the potential advantages of a more sensitive measurement during the early stages of disease progression, LCI2.5 will be used as a secondary endpoint in this study. LCI2.5 (the number of lung turnovers required to reduce the end tidal inert gas concentration to 1/40th of its starting value) represents the most commonly used MBW

parameter.

The safety assessments are standard parameters for clinical studies in drug development and are generally recognized as reliable, accurate, and relevant to the study of subjects with CF. OE assessments were added as part of safety monitoring.

OEs: A juvenile rat toxicity study performed to support dosing of IVA in subjects <2 years of age demonstrated lens opacities in some animals. Prior studies in rats and dogs of older age did not demonstrate similar findings. Given substantial differences between human and rat lens development, the finding is of unlikely relevance to humans. Periodic OEs for pediatric subjects receiving IVA or IVA in combination with a CFTR corrector are being performed to confirm this interpretation. The overall data acquired to-date do not suggest an association between IVA treatment and cataract development; however, a potential association has not been fully excluded.

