#### 11.5.5 Ophthalmologic Examination

Ophthalmologic examinations will be performed by a licensed ophthalmologist or optometrist.

The OE includes

- measurement of best corrected distance visual acuity of each eye; and
- pharmacologically dilated examination of the lens with a slit lamp.

If a cataract is identified and determined to be clinically significant by the ophthalmologist or optometrist, the subject's caregiver and the Vertex medical monitor will be notified.

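### The lens-opacity exclusion recognises only an ophthalmologist's judgement at screening, although an optometrist may do that examination and judge significance

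*Protocol*

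**What the plan says.** Exclusion 10 (Protocol 8.2) has two limbs. The first is a history of cataract or lens opacity. The second is "evidence of cataract/lens opacity determined to be clinically significant by a licensed ophthalmologist during the ophthalmologic examination (OE) at the Screening Visit". An examination from the 3 months before screening may stand in for the screening one if it meets protocol criteria. Children with documented bilateral lens removal are exempt.

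Table 3-1, footnote d, governs the screening examination: "An OE will be conducted by a licensed ophthalmologist or optometrist". Section 11.5.5 names the same two professions for eye examinations in general. It then says what follows when a cataract is found and is "determined to be clinically significant by the ophthalmologist or optometrist": the caregiver and the medical monitor are told. It states no other consequence.

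Two provisions turn these criteria into a decision. Section 8 says "Subjects who meet all of the inclusion criteria and none of the exclusion criteria will be eligible for the study". Table 3-2, footnote h, says "Randomization must only occur after all inclusion and exclusion criteria are met and before the first dose of study drug".

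**The concern.** The protocol authorises an optometrist to do the screening examination and to judge a cataract significant, but the exclusion that relies on this judgement counts it only when an ophthalmologist makes it. If an optometrist finds the opacity, the site has a finding of the kind exclusion 10 targets, yet the criterion's wording is not met.

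Two things are at stake. One is consistency: the same finding could exclude a child at one site and not at another, depending on which licensed examiner was available. The other is lens safety. Section 9.3.3 explains that the examinations were added because a juvenile rat study of ivacaftor showed lens opacities. It regards relevance to humans as unlikely and reports that the data so far "do not suggest an association between IVA treatment and cataract development; however, a potential association has not been fully excluded". A child enrolled with an existing opacity would also make later lens findings harder to interpret.

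**Working it through.** The protocol gives no figure to reproduce here, so the check is a comparison of the text.

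| Question | Provision | Answer |
|---|---|---|
| Who may do the screening eye examination? | Table 3-1, footnote d; Section 11.5.5 | Ophthalmologist or optometrist |
| Who may judge clinical significance, in general? | Section 11.5.5 | Ophthalmologist or optometrist |
| Whose judgement triggers exclusion 10 at screening? | Section 8.2, criterion 10 | Ophthalmologist only |
| What follows an optometrist's positive finding? | Section 11.5.5 | Caregiver and medical monitor are notified |
| Must an ophthalmologist confirm it? | No provision found | Not stated |

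The possible cases are then:

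1. **Opacity known before screening, or found in an accepted examination from the prior 3 months.** On its natural reading the history limb applies, whoever made the finding. The child is excluded.
2. **Opacity first found at screening and judged significant by an ophthalmologist.** The second limb applies. The child is excluded.
3. **Opacity first found at screening and judged significant by an optometrist.** The second limb fails on the examiner's profession. The history limb does not clearly apply: if it took in findings from the screening examination itself, the second limb and its significance test would do no work. The child meets no specific exclusion and, under Section 8 and footnote h, can be randomized if all else is in order.

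Only case 3 is a problem. The backstops for it are:

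- Exclusion 1 covers conditions that, in the investigator's opinion, might "pose an additional risk in administering study drug to the subject". It is discretionary and does not mention lens findings.
- Section 9.1.1.3 allows the screening window to be extended by one week to schedule an eye examination. It permits extra time but does not require a second examiner.
- Section 9.1.1.1 lists the exceptions to the ban on repeating failed screening assessments. The eye examination is not named among them.

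**Time to the next scheduled eye examination.** After screening, Table 3-2 schedules eye examinations at Week 48, Week 96, early termination and safety follow-up only. SAP Table 12-1 sets the Week 48 target at Day 337. From Day 1 that is 337 − 1 = 336 days, or 336 / 7 = 48 weeks. The examination may be done up to 7 days before the visit, so about day 329 after first dose for a visit on target (336 − 7 = 329).

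**The case against.** The strongest reply is that the two provisions do different jobs. Section 11.5.5 sets a wide trigger for notification, while exclusion 10 sets a stricter standard for exclusion. Both can hold together, with referral of an optometrist's positive finding implied. Reserving the decision for an ophthalmologist is a defensible choice. But the referral it depends on is not written anywhere, so the text needs a correction whichever intent is right.

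A second reply is that a bad outcome needs a long chain of events: no known opacity, an optometrist as examiner, a significant finding, no ophthalmologist consulted, a notified medical monitor who does not act, and an investigator who does not use exclusion 1. Section 11.2 also calls for assessment of disqualifying conditions from the medical history, Section 9.8 allows withdrawal from study drug for safety at any time, and the data monitoring committee reviews safety. This stands as an argument about size. It does not make exclusion 10 work as written, because these protections either rest on someone's judgement or act after enrolment.

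A third reply concerns the 336 days. That interval applies to every child and is not created by exclusion 10. A reported opacity would probably be followed sooner, full physical examinations that include the eyes fall on Day 1 and at Week 24, and about one third of children take placebo in Part 1. This is fair. The figure describes the scheduled examinations only and does not measure harm.

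**Conclusion.** The point holds. As worded, the screening limb of exclusion 10 misses a clinically significant opacity first found and judged by an optometrist, although the protocol authorises the optometrist to do both. This is an operative eligibility rule, so literal application has a consequence, but a small one. Few if any of about 50 children would be affected. The documents give neither the frequency of opacities at this age nor the share of screening examinations done by optometrists, so no rate can be derived.

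The conclusion assumes that the history limb covers what was known before the screening examination and not what is first seen at it, and that no referral to an ophthalmologist is implied. No efficacy result changes, and eye findings are only listed (Protocol 12.3.4.4; SAP 9.2.3.4 and 9.3.3.3). It is a minor correction, worth making because it is so cheap.

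**What to change.** In exclusion 10, change the examiner to *a licensed ophthalmologist or optometrist*, which matches Section 11.5.5 and Table 3-1, footnote d. This adds two words at the next amendment and leaves visits, sample size and analysis as they are.

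If the sponsor meant to reserve the decision for an ophthalmologist, the alternative is to keep exclusion 10 and add a sentence to Section 11.5.5 requiring an ophthalmologist to confirm an optometrist's positive screening finding before randomization. That also closes the gap, but a positive finding would then need a second appointment within the 28-day screening period or its one-week extension. The two-word change is simpler and uses a standard the protocol already accepts.

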## 9 STUDY IMPLEMENTATION

### 9.1 Study Design

This is a Phase 2, 2-part, randomized, double-blind, placebo-controlled, parallel-group study with a long-term open-label period in subjects 2 through 5 years of age with CF, homozygous for *F508del* (Figure 9-1).

**Figure 9-1 VX16-809-121 Study Design**

ETT: Early Termination of Treatment; IVA: ivacaftor; LUM: lumacaftor; pbo: placebo; q12h: every 12 hours.

- a The Safety Follow-up Visit is scheduled to occur 2 weeks ( $\pm 4$  days) after the last dose. The Safety Follow-up Visit is required for 1) subjects who complete their ETT Visit  $<10$  days after the last dose of study drug and 2) subjects who interrupt study drug treatment and complete their Week 96 Visit  $<10$  days after the last dose of study drug; it is not required for subjects who continue onto commercially-available, physician-prescribed study drug within 2 weeks ( $\pm 4$  days) of completing study drug treatment at the Week 96 or ETT Visit.
- b Approximately 50 subjects are planned to be randomized (2:1) to receive LUM/IVA or placebo. Subjects will receive LUM 100 mg/IVA 125 mg every 12 hours (q12h) (subjects weighing  $<14$  kg at screening), LUM 150 mg/IVA 188 mg q12h (subjects weighing  $\geq 14$  kg at screening), or matching placebo (Part 1 only) during the Treatment Period.
- c No downward dose adjustments will be made if a subject's weight decreases. If a subject subsequently weighs  $\geq 14$  kg at 2 consecutive visits, the dose will be adjusted to LUM 150 mg/IVA 188 mg q12h, at the second visit where weight  $\geq 14$  kg. Subjects who turn 6 years of age at or after the Week 48 Visit will receive LUM 200 mg/IVA 250 mg q12h (starting at the Week 48 Visit or the next scheduled visit after turning 6 years of age), regardless of weight.
- d Subjects who prematurely discontinue study treatment will have an ETT Visit as soon as possible.

### 9.1.1 Screening

Screening Visit assessments are listed in [Table 3-1](#).

Screening will occur within 28 days before administration of study drug. The investigator (or an appropriate authorized designee at the study site) will obtain informed consent from each subject's parent or legal guardian and the subject must sign an assent form (if applicable) before any study-specific procedures can be performed. The ICF (and assent form, if applicable) will comply with all applicable regulations governing the protection of human subjects and will be approved by Vertex and the site's institutional review board (IRB).

To prepare for study participation, subjects/caregivers will be instructed on the study restrictions (Section [9.4](#)).

#### 9.1.1.1 Repetition of Screening Assessments

Repetition of any individual Screening Visit assessment(s) that did not meet eligibility criteria is not permitted, with the following exceptions:

- If the subject cannot complete the MBW assessment (Section [11.4.2](#)).
- If there is clear evidence of a laboratory error (e.g., hemolyzed sample), equipment malfunction, or technician error, collection of a repeat sample for the appropriate laboratory test may be permitted after discussion with the Vertex medical monitor or authorized designee.
- Exclusionary liver function test (LFT) levels, which may be retested within 14 days of the original Screening Visit date.

In these cases, the individual assessment may be repeated during the Screening Period without repeating all the other Screening Visit assessments. Repetition of these screening assessments will not reset Screening Period window dates; however the Screening Period window may be extended by 1 week after approval by the medical monitor or authorized designee (Section [9.1.1.3](#)). If repeat values of the individual assessment(s) are within the eligibility criteria and completed within the Screening Period window, then the subject is eligible for the study.

